# **SAP** revision history

Date	Version	Justification for SAP version
05 September 2019	0.1	First draft for review
15 September 2019	0.2	Changes made for SAP reviewers'
		comments on v 0.1
21 September 2019	0.3	Changes made for SAP reviewers'
		comments on v 0.2
30 September 2019	1.0	Final version

# **1** Introduction

# 1.1 Trial background and rationale

Gestational diabetes is a type of diabetes that arises during pregnancy. Women with gestational diabetes have a two-fold increase in risk of pre-eclampsia and at least a seven-fold increase in risk of developing type 2 diabetes within 10 years . Gestational diabetes increases the risk of stillbirth and infants born to women with gestational diabetes are more likely to be large-for-gestational age, more likely to become obese during childhood, and more likely to become diabetic during adulthood .

Observational evidence suggests that a healthy lifestyle is associated with reduced risk of gestational diabetes in women with no history of the condition (here, a healthy lifestyle is defined as not smoking, maintaining a healthy body weight, consuming a healthy diet, and exercising regularly) .

Randomised controlled trial and observational evidence also suggests an active lifestyle is associated with a reduced risk of progression from gestational diabetes to type 2 diabetes (here, an active lifestyle is defined as taking part in at least 150 minutes per week of moderate-intensity physical activity or at least 75 minutes per week of vigorous-intensity physical activity).

### 1.2 Trial aim

The aim of this study is to assess the effectiveness of a structured education programme to improve physical activity in participants who have had gestational diabetes during any pregnancy up to 60 months (post birth) prior to recruitment, with the overall intention of reducing their risk of developing type 2 diabetes.

# 2 Methods

# 2.1 Trial design

The trial is a parallel group randomised controlled trial, in which participants are randomised to two groups (1:1). It will compare a structured education programme plus additional follow on support (a wrist worn activity monitor and interactive web based intervention) with usual care plus an information leaflet. The RCT will be conducted in two centres; University Hospitals of Leicester NHS Trust and George Eliot Hospital NHS Trust. Participants will be followed up for 12 months.

# 2.2 Randomisation

Randomisation will be stratified by age (<30years; ≥30years) and by ethnicity (White European; other) and participants will be randomised to either the control or the intervention arm.

# 2.3 Sample size

The primary outcome is based on increasing total physical activity as quantified by the Euclidean norm minus one (ENMO) method measured in milligravity units (mg). This is the

main measure of activity derived from the GENEActiv monitor. In order to detect a minimum clinically significant difference of 2.1 mg, which is equivalent to an overall increase in physical activity volume of approximately 30 minutes of brisk walking at 4km/h, assuming a standard deviation of 5.3 mg , a power of 80% and significance level of 5%, the sample size requires 202 participants. To allow for 20% loss to follow-up and 10% non-compliance of the GENEActiv monitor, we will therefore need to recruit 290 participants (145 in each arm).

# 2.4 Timing of final analysis

Analyses described in this SAP will be performed following completion of the trial and database lock.

# 2.5 Timing of outcome assessments

Outcomes will be assessed at 12 months, with intermediate assessments at 6 months which will include questionnaires and wearing the physical activity accelerometer.

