# 3.3 Analysis populations

#### 3.3.1 Complete Case Population

The level of missing data for each outcome will be assessed. If missing outcome data is present the initial analysis will be based on the complete cases as we have allowed 30% for loss to follow-up and non-compliance to GENEActiv monitor. All tests of the effect of treatment on outcomes will be conducted on a complete case (CC) population. That is, all the recruited participants will be included in the analysis, with the exception of those with

missing outcome data. This will be done on a 'by analysis' basis, i.e. only those participants with missing data for variables required for a specific analysis will be removed.

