#### (iv) Questionnaire measures

A number of different questionnaire measures will be completed by participants at baseline and 12 months. Details of these questionnaire measures are as follows:

- Recent Physical Activity Questionnaire (RPAQ) this will assess habitual physical activity in several domains including occupation, leisure, housework
- Health Related quality of life (EQ-5D-5L)
- 5-A-Day Consumption and Evaluation Tool (FACET) this will assess the participants' fruit and vegetable intake.
- Hospital Anxiety and Depression Scale (HADS14) this will assess the severity of symptoms of anxiety and depression.
- Jenkins Self-efficacy for Exercise Expectations Scale this will assess the ability to exercise.

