# 5.3 Analysis methods

#### 5.3.1 Analysis of primary outcome

The primary outcome is change in overall volume of physical activity (average acceleration, ENMO) from baseline to 12 months. For the primary outcome treatment arm will be compared using linear regression modelling with a binary indicator for randomisation group as the explanatory variable, terms for stratification factors (age and ethnicity) as confounders, and adjustment for the change in accelerometer wear time from baseline and overall volume of physical activity at baseline.

The primary analysis at 12 months will be based on complete data.

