#### 5.3.2.2 Intention-to-treat Population

To allow for full analysis set, missing data will be imputed using a multiple imputation procedure which substitutes predicted values from a regression equation. The imputation will be carried out by the MI command in Stata 15. MI replaces missing values with multiple sets of simulated values to complete the data, performs standard analysis on each completed dataset, and adjusts the obtained parameter estimates for missing-data uncertainty using Rubin's rules to combine estimates.

The following procedure will be followed:

• The MI will be set as wide

• The MI will register imputation of the overall volume of physical activity at 12 months and at baseline

• A regression method will be used , where the registered variables will be individually adjusted for the randomisation and stratification factors (age and ethnicity), with 100 imputations to avoid biased estimates, rseed (2259) and the force options

• MI estimate will provide the final results using the same regression model as the primary analysis and covariate adjustments.

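### Six-month accelerometry is scheduled but no stated analysis uses it, and the imputation model as written cannot correct dropout related to earlier activity

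*SAP*

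**What the plan says.** **Schedule.** SAP section 2.5 puts outcome assessment at 12 months, "with intermediate assessments at 6 months which will include questionnaires and wearing the physical activity accelerometer". No later section mentions 6 months.

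**Primary analysis.** Section 5.3.1 states: "The primary outcome is change in overall volume of physical activity (average acceleration, ENMO) from baseline to 12 months". The model is a linear regression on arm, the two stratification factors, change in wear time and baseline activity. The same section adds: "The primary analysis at 12 months will be based on complete data". Section 3.3.1 gives the reason: "the initial analysis will be based on the complete cases as we have allowed 30% for loss to follow-up and non-compliance to GENEActiv monitor".

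**Imputation.** Section 5.3.2.2 is the intention-to-treat sensitivity analysis. On what is imputed: "The MI will register imputation of the overall volume of physical activity at 12 months and at baseline". On the predictors, it describes a regression method "where the registered variables will be individually adjusted for the randomisation and stratification factors (age and ethnicity), with 100 imputations". The primary regression is then fitted to the completed data.

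**Other analyses.** The per-protocol analysis (5.3.2.1) follows the primary steps. The valid-day models (5.3.2.3) and the secondary analyses (5.3.3) name no 6-month time point.

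**Questionnaires.** Section 5.2 (iv) says: "A number of different questionnaire measures will be completed by participants at baseline and 12 months". Section 2.5 includes questionnaires at 6 months.

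**The concern.** The 6-month accelerometer value is likely to be the best available predictor of a missing 12-month value, and the plan gives it no role. The reason offered for complete cases is a sample-size reason. Recruiting 290 so that about 202 remain keeps the power, but it does not make those who remain comparable between arms. Section 3.2 itself recognises missing values as a potential source of bias.

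The trial compares an education programme with a leaflet, and participants are likely to know which they received, so women may leave the two arms for different reasons. If women in the programme who are doing poorly at 6 months tend not to return, the 12-month contrast among completers is too favourable. The imputation analysis is the plan's check on this. If its model carries no information on earlier activity, it cannot detect or correct the problem, and its agreement with the primary result would give false reassurance.

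**Working it through.** **1. The plan's own figures.** Inputs from SAP section 2.3: difference 2.1 mg, SD 5.3 mg, power 80%, level 5% (two-sided by section 3.1), 1:1 allocation.

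- Normal approximation: 2 × (1.960 + 0.842)² × 5.3² / 2.1² = 100 per arm.
- The t-test version gives 101 per arm, so 202, as stated.
- Inflation: 202 / (1 − 0.30) = 288.6, so 289, rounded to 290 for equal arms.

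The sample size reproduces and is not at fault.

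**2. Women outside the primary analysis.** 0.30 × 290 = 87. (290 − 202 = 88; the difference is rounding.)

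**3. What each analysis conditions on.**

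| Analysis | Baseline activity | 6-month activity |
|---|---|---|
| Primary regression, 5.3.1 | yes | no |
| Imputation model, 5.3.2.2 as written | apparently not | no |
| Imputation proposed below | yes | yes |

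The wording on individual adjustment is read here as one regression per activity value on arm, age and ethnicity. On that reading the imputation model holds less than the model it feeds, because the final regression adjusts for baseline activity and the imputation of 12-month activity does not.

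**4. Bias by simulation.** From the SAP: SD 5.3 mg and difference 2.1 mg (used at both follow-up visits). The SAP gives none of the following, so these are assumptions: equal correlations of 0.5 to 0.7 between visits; about 30% missing at 12 months; in the intervention arm only, the log-odds of dropout rise by 0.5 to 1.0 for each SD of lower 6-month activity. Strata and wear time were not simulated.

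| Method | Bias in the 12-month difference |
|---|---|
| Complete cases, adjusted for baseline | about +0.15 to +0.38 mg |
| Imputation from arm only | about +0.4 to +1.0 mg |
| Conditioning on baseline and 6-month activity, every dropout has a 6-month value | about 0 |
| The same, half of the dropouts have one | about 0.06 to 0.16 mg |
| Complete cases, same dropout mechanism in both arms | about 0 |

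As a share of the target difference, complete-case bias is 0.15 / 2.1 = 7% to 0.38 / 2.1 = 18%. Imputation from arm only gives 0.4 / 2.1 = 19% to 1.0 / 2.1 = 48%. It does worse than complete cases because baseline adjustment absorbs part of the selection, whereas this imputation fills in the women who left at the average of those who stayed in their arm.

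For scale, the standard error of the difference with 101 per arm is 5.3 × √(2/101) = 0.75 mg. Complete-case bias is therefore 0.2 to 0.5 of a standard error.

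**5. Precision.** Let r be the correlation of 6- and 12-month activity given baseline, and f the share of women missing at 12 months who have 6-month data (both assumed). The variance ratio is 1 − r²(1 − n₁₂/n₆), with n₁₂ = 101 per arm and n₆ = 101 + 44f. For r = 0.5 and f = 0.5, n₆ = 123, the ratio is 0.955, the effective size is 105.7 per arm, and power rises from 80.4% to 82.1% (normal approximation). Across r from 0.3 to 0.7 and f from 0.25 to 0.75, power is 80.7% to 85.1%. The gain is modest; the case rests on bias.

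**6. Questionnaires.** Section 2.5 includes questionnaires at 6 months. Section 5.2 (iv) places them at baseline and 12 months. The opening line of 5.2 speaks only of baseline and follow-up, which settles nothing.

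**The case against.** The case on the other side is substantial.

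- **The primary model is an accepted analysis.** Baseline-adjusted regression on complete cases is valid when missingness depends only on arm, strata and baseline activity. Leaving an intermediate visit out of it is not an error. This stands. A reader might infer that the primary model must be replaced by a mixed model of all three visits. The document does not support that: it is a trade-off, and a mixed model with only arm by visit, strata and a covariance structure would lose the wear-time adjustment of section 5.3.1.
- **The missing women are not abandoned.** A reader might infer that a woman without 12-month or baseline accelerometry contributes nothing. That is true only of the complete-case analyses; section 5.3.2.2 imputes both values. What remains is that its model omits the information that matters.
- **The bias is conditional.** It needs dropout to depend on 6-month activity differently by arm, and the SAP gives no sign of this either way. This stands. The size also depends on the model: a simpler simulation without a baseline term, with 6-to-12-month correlations of 0.3 to 0.7, gave complete-case estimates of 2.3 to 3.1 mg against a true 2.1 mg.
- **Full correction is a best case.** The allowance in section 2.3 includes 10% monitor non-compliance, and those women may lack 6-month wear too. This stands, and is why the half-observed case is shown.
- **The questionnaire clash is small.** Section 5.2 (iv) does not say that questionnaires are completed only at those two times, and section 2.5 does not say which are given at 6 months. It is a matter of wording and does not touch the primary result.

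**Conclusion.** The point holds in a limited form. The plan schedules 6-month accelerometry and gives it no analysis. It defends complete cases by an allowance that concerns power. Its imputation check, as written, cannot correct dropout related to earlier activity.

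Under arm-specific dropout of the assumed strength, the primary estimate would be about 7% to 18% of the target difference too high, and the imputation estimate further off than the primary one. If both arms share the mechanism, the bias is about 0. So the document does not show that the primary estimate will be biased, only that the planned safeguard is weak where it would be needed.

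The 30% should also not be read as a ceiling. It is a planning figure, and actual exclusions may be lower or higher. The second table in the working rests on assumed correlations and dropout slopes. The reading of the imputation model rests on the wording about individual adjustment, which the sponsor can confirm or correct.

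**What to change.** - **Section 5.3.2.2:** impute baseline, 6-month and 12-month activity jointly, for example by chained equations run separately by arm. Each value should predict the others, with the stratification factors and wear time also in the model. Wear time needs a stated rule, because the final regression adjusts for its change and it may be missing for the same women.
- **Section 5.3.1:** keep the primary model. A mixed model of baseline, 6 and 12 months with a 12-month contrast may be added as a supportive analysis if it keeps the wear-time adjustment.
- **Section 3.3.1:** do not offer the recruitment allowance as the reason for complete cases. State the missing-data assumption instead.
- **Sections 5.2 and 5.3.3:** say whether 6-month results are reported as secondary outcomes.
- **Sections 2.5 and 5.2 (iv):** reconcile which questionnaires, if any, are completed at 6 months.

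The cost is a few lines of SAP text and a little more analysis work. It needs no data beyond those already scheduled.

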# 3 Statistical principles

### 3.1 Confidence intervals and p-values

The estimates of effect will be reported with 95% confidence intervals, for both primary and secondary outcomes. All p-values shown will be two sided.

# 3.2 Missing values and outliers

Missing values represent a potential source of bias in clinical trials. Therefore, every effort will be made to ensure the data is fully explored for potential problems and have been correctly entered into the database. Participants who did not attend the baseline assessment after consent will be excluded from all analyses, but will be noted on the CONSORT flow chart. For the primary and secondary analyses, participants who do not have an outcome measurement will be excluded; as discussed in section 3.3.1. Sensitivity analyses will be performed to assess the robustness of the findings to missing data (detail in section 5.3.2).

Outliers will be identified by examining graph plots such as normality plots, box plots and histograms. Values that visually appear outside of the main distribution (i.e. outliers) will be further investigated and if this is the correct observation it will remain in the analysis, however further assumptions will be made to assess possible influences on the results using a sensitivity analysis; by removing the outlier or outliers to compare results. Where results from the two analyses are discrepant, this fact will be reported and discussed in the study publication.

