#### 3.3.2 Intention-to-treat Population /Full analysis data

A sensitivity analysis using multiple imputation will be used to impute missing data, to assess the robustness of the conclusions to missing data. This will be a full intention to treat analysis. More detail is in section 5.3.2.2.

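### The multiple imputation assumes at least as much about missing outcomes as the complete-case analysis it checks, so a short delta-adjusted analysis should be added once the imputation model is repaired

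*SAP*

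**What the plan says.** SAP 3.2 leaves anyone without an outcome measurement out of the primary and secondary analyses, then undertakes that "Sensitivity analyses will be performed to assess the robustness of the findings to missing data", with details in 5.3.2. Section 3.3.1 gives the reason for starting from complete cases: "the initial analysis will be based on the complete cases as we have allowed 30% for loss to follow-up" and for monitor non-compliance. Section 3.3.2 adds multiple imputation "to assess the robustness of the conclusions to missing data".

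The primary model (5.3.1) is a linear regression with arm, the age and ethnicity strata, wear-time change and baseline activity as terms.

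Section 5.3.2 then lists three sensitivity analyses:

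- **Per-protocol (3.3.3 and 5.3.2.1):** requires complete outcome data.
- **Multiple imputation (5.3.2.2):** imputes baseline and 12-month activity, each from arm, age and ethnicity, with 100 imputations, and refits the primary model with its covariates.
- **Valid days (5.3.2.3):** restricts to participants with at least 2, 3 or 4 valid days of wear.

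Section 2.5 says the accelerometer is also worn at 6 months. That measurement is not among the imputation predictors. The SAP states no missing-data mechanism.

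**The concern.** Of the three analyses, only the imputation gives values to participants who have no 12-month outcome. It draws those values from regressions fitted to participants who were observed, so it treats a non-returner as exchangeable with returners of the same arm, age group and ethnicity. The complete-case regression already makes an assumption of that kind, conditional on more information. The check therefore cannot disagree with the primary result for the reason that matters most: that women who did not return, or did not wear the monitor, differ from those who did in ways the recorded covariates do not capture.

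In a trial of an activity programme against a leaflet, it is plausible that return and monitor wear are related to how active a woman has become. The plan could report its result as robust to missing data without having examined this. The reason given in 3.3.1 does not help, because recruiting more participants restores precision and leaves any selection unchanged.

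**Working it through.** **1. Inputs, SAP 2.3, 2.1 and 3.1.** A "minimum clinically significant difference of 2.1 mg"; "assuming a standard deviation of 5.3 mg"; "a power of 80% and significance level of 5%, the sample size requires 202 participants"; two arms, 1:1; two-sided tests; losses of 20% (follow-up) and 10% (monitor non-compliance); 290 to be recruited, 145 per arm.

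**2. Reproduce the plan's figures.** Normal approximation: n per arm = 2 × (1.96 + 0.8416)² × 5.3² / 2.1² = 100. The t-test version gives 100.96, so 101 per arm and 202 in all, as stated. Then 202 / 0.70 = 288.6, so 289, rounded to 290 for equal arms. Treating the losses as successive gives 202 / (0.8 × 0.9) = 281, which does not match. The 30% is thus the SAP's own additive allowance.

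**3. Compare the assumptions.**

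| Analysis | What missingness may depend on |
|---|---|
| Complete-case primary model (5.3.1) | arm, age, ethnicity, baseline activity, wear-time change |
| Imputation (5.3.2.2) | arm, age, ethnicity |

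The second list is a subset of the first, so the imputation is no less demanding than the analysis it checks. The 6-month activity could have relaxed the assumption but is not used.

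**4. Who enters the refitted model.** The primary model needs wear-time change. Section 5.3.2.2 names only baseline and 12-month activity as variables to impute. A participant with no 12-month recording has no 12-month wear time, so on a literal reading she drops out of the refitted model even after her activity has been imputed.

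**5. Size of a shift.** Let m be the fraction missing in the intervention arm and δ the amount by which its missing participants fall below their imputed mean, with no shift in the control arm. The all-randomised effect is then the unshifted effect minus m × δ. Take an unshifted effect of 2.1 mg and δ = 2.1 mg (non-returners gained nothing):

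- m = 0.20: 0.20 × 2.1 = 0.42 mg, leaving 1.68 mg.
- m = 0.30: 0.30 × 2.1 = 0.63 mg, leaving 1.47 mg.
- Equal m and δ in both arms: mδ − mδ = 0.

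**6. Where the interval reaches zero.** With 101 observed per arm, SE = 5.3 × √(2/101) = 0.746 mg and the 95% CI is 2.1 ± 1.96 × 0.746, or 0.64 to 3.56 mg. Holding that SE fixed, the lower limit reaches zero at δ = 0.638 / 0.30 = 2.13 mg (30% missing) or 0.638 / 0.20 = 3.19 mg (20% missing). The estimate itself reaches zero at 2.1 / 0.30 = 7.0 mg or 2.1 / 0.20 = 10.5 mg.

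**7. Simulation.** Settings: 290 participants, 30% missing in each arm, shift in the intervention arm only, assumed baseline to 12-month correlation 0.6, 600 runs, 20 imputations. Wear time was left out, so non-returners did re-enter the model.

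| δ (mg) | All-randomised effect (mg) | Complete case (mg) | Imputation as in 5.3.2.2 (mg) |
|---|---|---|---|
| 0 | 2.10 | 2.11 | 2.09 |
| 2.1 | 1.47 | 2.05 | 2.05 |
| 5.3 | 0.51 | 2.10 | 2.10 |
| 7.0 | 0.00 | 2.08 | 2.09 |

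The two analyses agree in every row, whatever the all-randomised effect.

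**The case against.** The strongest reply is that the SAP promises robustness to missing data in general, not to informative drop-out. Complete cases followed by multiple imputation is a common pairing, and no sentence of the SAP becomes false without a further analysis. That stands as far as the grade goes: this is an improvement to the plan, not the correction of a false statement. It does not remove the point, because a check that assumes at least as much as the thing checked does little for the purpose the SAP gives it.

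Three stronger readings are tempting, and the documents do not support them.

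- **That 30% of outcomes will be missing.** The figure is a recruitment allowance. Section 5.2(i) admits a participant with one valid day, which should limit losses from non-wear.
- **That drop-out will be informative, mainly in the intervention arm.** Nothing in the SAP says so. The one-arm shift is an assumption, and similar loss and shift in both arms would largely cancel.
- **That the effect could fall by 0.30 × 5.3 = 1.59 mg.** This puts every missing intervention participant a full 5.3 mg below prediction, about 2.5 times the target difference. The 5.3 mg is the standard deviation used for sample size, not an expected deficit among non-returners.

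It is also fair to say that a delta adjustment bolted onto 5.3.2.2 as written might change nothing, because non-returners may not enter the refitted model. That is accepted, and it sets the order of the fix.

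**Conclusion.** The point holds as a cheap improvement. The only analysis that fills in missing outcomes conditions on a subset of the primary model's covariates. It therefore cannot examine informative drop-out, and its agreement with the complete-case result should not be reported as evidence on that question. The allowance in 3.3.1 is a reason about power, not about bias.

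The illustrative size is a fall of 0.42 to 0.63 mg in a 2.1 mg effect. This rests on three assumptions: missingness at the 20% to 30% allowance, missing intervention participants gaining none of the effect, and no shift in the control arm. At 30% the remaining 1.47 mg is borderline (1.47 / 0.746 = 1.97); at 20% the remaining 1.68 mg is not (1.68 / 0.746 = 2.25). Both ratios hold the standard error at its value for 101 per arm and take no credit for baseline adjustment.

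A reader might infer that the primary analysis is biased or should be replaced. The documents do not show that. The complete-case analysis can remain primary; what is missing is a way to see how far its conclusion depends on its assumption.

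**What to change.** 1. **Repair 5.3.2.2 first.** Impute baseline and 12-month activity jointly, with arm, the strata and 6-month accelerometer activity as predictors. Either impute 12-month wear time as well, or leave the wear-time change term out of the model fitted to imputed data, and state which. Non-returners then enter the refitted model.
2. **Add a pre-specified delta-adjusted analysis.** Shift imputed 12-month ENMO separately by arm over a stated grid, for example 0 to −5.3 mg, extended if needed. Refit the model at each combination. If the unshifted 95% confidence interval excludes zero, report the shift at which it first includes zero.
3. **Amend 3.3.1.** Remove the sample-size allowance as the reason for complete cases, and state the assumption under which the complete-case model is valid.

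The cost is a revised paragraph in 5.3.2.2, a loop over the repaired imputations and one more table. The range of shifts is a judgement, so it should be fixed before the results are seen.
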